7.4 Withdrawal of individual subjects

Subjects can leave the study at any time for any reason without any consequences. The investigator can decide to withdraw a subject from the study for urgent medical reasons.

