Risks: There are no additional risks or burdens to the patients participating in this post market observational cohort study. The implantation of the system and collection of follow up data is a standard procedure in dedicated neuromodulation Pain Clinics in The Netherlands. The data collected consists of standard questionnaires on pain relief, quality of life, physical functioning, subject safety and subject satisfaction.

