4.4 Sample size calculation

As this is a post market observational cohort study, no sample size calculations are necessary. We aim to enrol 30 subjects in this cohort.

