7.5 Replacement of individual subjects after withdrawal

Subjects that are withdrawn during the study will not be replaced.

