7.6 Follow-up of subjects withdrawn from treatment

Any patient leaving the study will receive standard follow-up care in accordance with the criteria of the Dutch Neuromodulation Society.

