9.2 Analysis

Univariate, multivariate and covariate statistical analyses will be conducted as appropriate to statistically tests for both primary and secondary outcomes. Statistical analyses will be conducted utilizing SAS and/or SPSS statistical software. *Post-hoc* power analyses will also accompany the omnibus testing and *post-hoc* analyses determining differences

between baseline and treatment means. All levels of significance will be deemed to occur at $p<0.05$.

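### Section 7.4 allows withdrawal from the study, not only from treatment, for undefined urgent medical reasons, and no scheduled outcome or new-AE collection is provided for afterwards

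*Combined protocol and SAP*

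**What the plan says.** Section 7.4 lets subjects leave whenever they wish and adds an investigator rule: "The investigator can decide to withdraw a subject from the study for urgent medical reasons". The section does not say what counts as urgent or medical, or whether any data are collected afterwards.

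Section 7.6 is headed "7.6 Follow-up of subjects withdrawn from treatment". Its only sentence is about something else: "Any patient leaving the study will receive standard follow-up care in accordance with the criteria of the Dutch Neuromodulation Society". It names no study assessment.

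Section 7.5 adds: "Subjects that are withdrawn during the study will not be replaced". Section 4.4 sets the size: "We aim to enrol 30 subjects in this cohort".

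The Summary, under Risks, describes participation this way: "There are no additional risks or burdens to the patients participating in this post market observational cohort study". Section 10.3 says that the questionnaires are ones already used under the Dutch Neuromodulation Society criteria.

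**The concern.** The study assigns no treatment. By its own account it adds only standard questionnaires and adverse event recording, at no extra risk. A medical emergency may be a reason to change care, but ending data collection protects nobody. Such an emergency may also be exactly what the device-safety objective is meant to capture.

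If section 7.4 is followed as written, a subject can lose the remaining VAS, EQ-5D, BPI and new-AE assessments for a medical reason. That reason may be related to the outcome, so the subjects still observed at 24 months may differ systematically from all those implanted. Section 9 has no rule for withdrawn subjects or missing visits. A sensitivity analysis could bound the effect but could not restore measurements that were never taken.

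**Working it through.** **Step 1. What continues after an investigator withdrawal**

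| Data | Where | After withdrawal |
|---|---|---|
| SAEs already recorded | 8.3 | Followed to an outcome or stable state; loss to follow-up is the only exception |
| Device-related AEs already recorded | 8.3 | Followed until gone or stable |
| AEs not device-related | 8.3 | Followed to the end of the study, which is not defined for a withdrawn subject |
| New AEs | 8.2 | Not provided for: AEs are events during the study, asked about at study visits |
| VAS, EQ-5D, BPI | 7.3, Appendix A | Not provided for: tied to scheduled visits |

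Two other places come close but do not close the gap.

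- Section 7.7 keeps safety monitoring going for as long as the device is in use. It concerns early termination of the whole study, and does not clearly reach one withdrawn subject or one whose device is removed.
- The interim-visit part of section 7.3 covers revision, replacement and explant within the cohort. It does not make explant an exit, but it also does not say that the scheduled visits continue afterwards.

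**Step 2. Possible size for pain**

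The plan has no figure to reproduce: section 4.4 gives a target of 30 without a calculation, and no dropout rate appears. All inputs below are assumptions.

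- Implanted subjects: n = 25
- Mean 24-month VAS in subjects who remain: 35 mm
- Mean 24-month VAS in withdrawn subjects, had it been measured: 75 mm
- Withdrawn subjects: w = 1, 2 or 3

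The mean in all implanted subjects is [35 × (25 − w) + 75 × w] / 25. The observed mean is 35. The difference is (w / 25) × 40:

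- w = 1: 1.6 mm
- w = 2: 3.2 mm
- w = 3: 4.8 mm

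In general the difference is (w / n) × d, where d is the mean improvement in completers minus that in withdrawn subjects. Over a wider assumed range:

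- n = 30, w = 1, d = 20 mm: 20 / 30 = 0.7 mm
- n = 24, w = 3, d = 20 to 40 mm: 2.5 to 5.0 mm
- n = 18, w = 5, d = 40 mm: 200 / 18 = 11.1 mm

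If withdrawn subjects had the same relief as the others, d = 0 and there is no bias. If they had better relief, the sign reverses.

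**Step 3. Possible size for safety observation**

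Assume withdrawal at month 6, so 24 − 6 = 18 months are lost per subject. Planned follow-up is 25 × 24 = 600 subject-months. Losses for w = 1, 2 and 3 are 18, 36 and 54 subject-months, or 3%, 6% and 9%. This is time in which new events are not sought. Serious or device-related events already recorded are still followed.

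**The case against.** The strongest case against is that the protocol covers more than sections 7.4 and 7.6 suggest. Three stronger readings are tempting, and the documents support none of them.

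- **That safety data stop.** Section 8.2 records all AEs regardless of cause, so the event that prompts a withdrawal is captured. If it is serious or device-related, section 8.3 follows it to an outcome or stable state, and withdrawal is not listed as an exception. What is left uncovered is new events and the end point for AEs not related to the device.
- **That leaving treatment means leaving the study.** Section 7.6 does not say so. Its heading and text do not match, which leaves the question open. Section 7.3 deals with explant during the cohort.
- **That the subjects lost are those with the worst outcomes.** The rule is permissive and its reasons are undefined. An urgent medical reason could be unrelated to pain or to the device, in a subject with good relief.

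It is also fair to object that every input to the illustration is assumed, and that 75 mm presumes substantial residual pain, above the 60 mm entry minimum. On cost, the documents do not show that explanted subjects keep the standard schedule to 24 months, so continued assessment may add visits for them.

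These objections limit the claim but do not remove it. No section provides for scheduled outcomes or new-event detection after an investigator withdrawal, and the trigger is a medical one.

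**Conclusion.** The point holds as a gap in data collection. Section 7.4 permits removal from the study for undefined medical reasons, section 7.6 does not separate stopping treatment from leaving the study, and VAS, EQ-5D, BPI and new-AE collection is not provided for afterwards. With about 30 subjects and no replacement, even a few such withdrawals could affect the 24-month results.

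The direction is plausibly favourable to the device, on the assumption that subjects withdrawn for medical reasons tend to do worse. The size cannot be derived from the documents: 1.6 to 4.8 mm for 1 to 3 of 25 shows scale only and is not an expected bias. This is a cheap improvement, not a defect that invalidates the study.

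**What to change.** Change the wording on data collection only, with no new rule on device use.

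- State in sections 7.4 and 7.6 that a medical event, or a device that is off or removed, does not end study data collection.
- Keep such subjects on the remaining scheduled assessments and AE collection to 24 months, with AEs taken by telephone if a visit is not possible. The exceptions are withdrawal of consent, death and loss to follow-up.
- Reconcile the heading and text of section 7.6.
- State how section 8.3 applies after withdrawal, including where follow-up ends for AEs not related to the device.

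The cost is protocol wording and a few more questionnaires, possibly beyond standard care for explanted subjects. The 24-month mean and AE rate would probably look slightly less favourable.

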7.5 Replacement of individual subjects after withdrawal

Subjects that are withdrawn during the study will not be replaced.

7.6 Follow-up of subjects withdrawn from treatment

Any patient leaving the study will receive standard follow-up care in accordance with the criteria of the Dutch Neuromodulation Society.

7.7 Premature termination of the study

The Post Market Observational Cohort Study will be terminated prematurely if the Investigators feel there is a risk to the subjects enrolled. Subject safety will continue to be monitored by the Investigators for the duration of the device.

8 SAFETY REPORTING

8.1 Applicable local laws and regulations

All AEs and SAEs will be reported according to the applicable local laws and regulations for CE marked products

8.2 Adverse and serious adverse events

Adverse events are defined as any undesirable experience occurring in a subject during the study, whether or not considered to be related to the Spinal Modulation DRG Neurostimulator System. All adverse events reported spontaneously by the subject or observed by the investigator or his staff will be recorded.

Adverse events related to the commercially available Spinal Modulation DRG Neuromodulation System will be reported to Spinal Modulation representatives and handled according to the Spinal Modulation internal vigilance regulations for CE marked products.

Clinical study staff will start assessing subjects for adverse events (AEs) once the Informed Consent form has been signed and at each visit thereafter. They will be instructed to request AE information in a nonspecific, non-suggestive manner. Investigators will report all AEs regardless of causality.

Serious Adverse Events (SAE):

A serious adverse event is any untoward medical occurrence or effect that:

- results in death;
- is life threatening (at the time of the event);
- requires hospitalization or prolongation of existing inpatients' hospitalization;
- results in persistent or significant disability or incapacity;
- is a congenital anomaly or birth defect;
- is a new event in the cohort likely to affect the safety of the other study subjects, such as an unexpected outcome of an adverse reaction, major safety finding from a newly completed animal study, etc.

Important medical events that may not result in death, be life-threatening, or require hospitalization may be considered an SAE when, based upon appropriate medical judgment, they may jeopardize the patient and may require medical or surgical intervention to prevent one of the outcomes listed in this definition.

For the purposes of this study the following events will not be reported as serious adverse events due to the nature of the treatment.

- Prolonged hospitalization as a result of a revision procedure, which is allowed in the protocol.
- Hospitalization as a result of or in conjunction with treatment that is part of the subject's conventional medical management.

All SAEs must be reported within 24 hours of the investigational site's knowledge of the occurrence by entering the required information into the appropriate CRF.

The following SAE information will be provided as available:

- Patient ID;
- SAE term, onset date, severity, and causal relationship;
- Basic demographic information (e.g., age, gender, etc.);
- The outcome(s) attributable to the event (death, life-threatening, inpatient hospitalization or prolongation of existing hospitalization, persistent or significant disability/incapacity, congenital anomaly/birth defect or other important medical event(s));
- A summary of relevant test results, pertinent laboratory data, and any other relevant medical history;

- Date study device was implanted;
- Supplemental information may include, but may not be limited to, the following records: laboratory results, progress notes, admission and emergency room notes, discharge summaries, autopsy reports, death certificates, etc.

The Investigator will report all SAEs in accordance with the regulatory reporting requirements. Documentation will be provided to the sponsor.

For each AE or SAE the following information will be recorded on the appropriate CRF:

- Name of event: The Investigator should use standard medical terminology that clearly describes the pathophysiology of the event and identifies the body system affected.
- Onset date: Date that the AE was first experienced at the reported severity and frequency.
- Resolution date: Date that the AE was last experienced or was completely resolved. In the case of an AE that changes in severity or frequency, the resolution of the AE is the date it was last experienced at the previously reported severity.
- Severity: All AEs will be graded according to the following:
 - Mild, easily tolerated by the subject, causing minimal discomfort and not interfering with every day activities;
 - Moderate, sufficiently discomforting to interfere with normal every day activities;
 - Severe, prevents normal, everyday activities; Life threatening, places the subject in immediate risk of death
- Relationship to study device: All AEs will have a study device causality assessment performed at the time of reporting the event to document the Investigator's perception of causality. As stated in the ISO standards, adverse events classified as device-related should involve one of the following:
 - Insufficient or inadequate instructions for use
 - Deployment of the device
 - Implantation of the device
 - Operation of the device
 - Malfunction of the device
 - Misuse of the device

If the Investigator feels the AE is related to the implant procedure and related or possibly related to the device, he/she should assign causality to either "Related to the Device" or "Possibly related to the Device."

Unexpected Adverse Device Event (UADE)

Unexpected adverse reactions are adverse events, of which the nature, or severity, is not consistent with the applicable product information (e.g. *IFU*).

UADEs will be reported to regulatory authorities as is outlined and required by law.

Expedited reporting will occur in the timeframes that regulatory authority deems appropriate.

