Subjects will be followed according to the standard follow-up schedule for 24-months following implant at regular intervals: 1-week (± 5 days), 4 weeks (± 1 week), 3 month (± 2 weeks), 6 month (± 2 weeks), 12 months (± 2 weeks) and 24 months (± 2 weeks). The given time-windows are advisable and therefore visits outside the time windows will not be seen as a protocol deviation. If desired, the Investigators may contact the subjects telephonically for evaluations at 8-weeks, 9-months and 18 months post-implant.

Prior to completing the required measurements, the subject will have his/her stimulator reprogrammed if needed or applicable.

24-month follow-up (Study Exit)

The study will end 24 months following INS implantation. At this visit, the regular follow-up assessments as outlined in appendix A will be acquired and a trial exit form will be completed.

Following completion of the study, subjects will continue to use the Spinal Modulation DRG Neurostimulator System. They will be monitored by their physician in accordance with standard medical procedures.

Interim Programming/Revision/Replacement/Explant (if necessary)

During the course of the cohort, subjects will have the option to return to the study site at any time to have their neurostimulator re-programmed to achieve maximal benefit. If any part of the Spinal Modulation Neurostimulator System becomes dysfunctional or requires adjustment following implantation, the patient will come to the site for analysis of the problem (interim visit). In appendix A, the assessments are listed for an interim visit and a revision (if applicable).

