8.3 Follow-up of adverse events

All adverse events determined to be device related will be followed until they have abated, or until a stable situation has been reached. All AEs determined to not be device related will be followed through the end of the study. All SAEs, regardless of the relationship to the device will be followed until resolution or stabilization unless the subject is lost to follow-up. Depending on the event, follow up may require additional tests or medical procedures as indicated, and/or referral to the general physician or a medical specialist.

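### The SAE exemption for prolonged hospitalisation after a revision is not limited to the planned, uncomplicated stay, so a revision complication that is serious only because it prolongs the stay may not be counted as an SAE

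*Combined protocol and SAP*

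**What the plan says.** Section 8.2 of the combined protocol and SAP defines an SAE as an untoward medical occurrence or effect that meets one of several criteria. One is that it "requires hospitalization or prolongation of existing" inpatient stays. An important-medical-event clause follows: "Important medical events that may not result in death, be life-threatening, or require hospitalization may be considered an SAE when" medical judgment supports it.

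The section then sets two exceptions, introduced by "For the purposes of this study the following events will not be reported as serious adverse events due to the nature of the treatment". The first is "Prolonged hospitalization as a result of a revision procedure, which is allowed in the protocol". The second concerns hospitalisation linked to conventional medical management and is not the subject of this point.

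Two consequences depend on the SAE label. Section 8.2 sets a reporting clock for SAEs: "All SAEs must be reported within 24 hours of the investigational" site learning of the event. Section 8.3 sets follow-up: "All SAEs, regardless of the relationship to the device will be followed until resolution or stabilization unless the subject is lost to follow-up". For events without the label, section 8.3 separates device-related events, which are followed until they have abated or are stable, from the rest: "All AEs determined to not be device related will be followed through the end of the study". Section 7.3 fixes that end: "The study will end 24 months following INS implantation".

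Revisions are foreseen. Section 7.3 provides for them when a component fails or needs adjusting, and Appendix A gives revision its own form (CRF-14) and its own column. Device safety is a secondary objective in section 2.

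**The concern.** The criterion and the exemption meet on the same event. A hospital stay of the expected length would not normally be called prolonged, whereas a stay extended by a complication would. The exemption as worded therefore reaches the very stays that the criterion is meant to catch, and it contains no word such as planned, routine or uncomplicated to hold it back.

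At stake is the consistency of the SAE count, which is part of how the study would describe device safety. An event that meets the protocol's own seriousness criterion could be left out of the count at one site and included at another. Where it is left out, entry on the SAE form within 24 hours is not required. Section 8.4 states that there is no data safety monitoring board, and sections 11.3 and 11.4 state that no progress or final report goes to the ethics committee. Few later steps would therefore bring a difference in classification to light.

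**Working it through.** The documents state no figure on this point, so there is none to reproduce. The check is a reading of the relevant text, with two small calculations for scale.

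**Step 1: is the exemption limited anywhere?** The lead-in gives a reason (the nature of the treatment) but no condition. The clause about what the protocol allows does not narrow the exemption either, because section 7.3 allows a revision whenever any part of the system stops working properly or needs adjustment. Sections 8.1, 8.3, 8.4 and 9 and Appendix A add no limit.

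**Step 2: which events fall inside it?** An event is affected if it:
- arises from a revision and prolongs that hospital stay;
- meets no other seriousness criterion (death, threat to life, disability and so on);
- is not raised to an SAE by the investigator under the important-medical-event clause, which is permissive.

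The wording is causal and concerns a prolonged stay. It does not cover a new admission.

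**Step 3: what changes for such an event?**
- *SAE label:* given under the criterion; withheld under a literal reading of the exemption.
- *24-hour CRF entry:* required for SAEs; not required otherwise.
- *Follow-up if device-related:* until abated or stable, so little changes.
- *Follow-up if not device-related:* an SAE is followed to resolution or stabilisation; a non-serious event is followed only to study end.
- *Items recorded:* for every AE, section 8.2 lists name, onset, resolution, severity and relationship to the device. Prolongation of a stay appears only in the list of SAE information. The CRFs are not shown, so whether the AE form also holds it is unknown.

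**Step 4: do other routes restore the label or the clock?** Vigilance reporting covers device-related events. The unexpected-device-event route covers events whose nature or severity does not match the product information. Section 8.1 requires reporting of AEs and SAEs under local law for CE-marked products. All three continue to apply, but none requires the study's SAE label or the 24-hour CRF entry.

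**Step 5: scale.**
- *Effect of one subject.* Section 4.1 plans 30 subjects. One subject whose only serious event is exempted changes the proportion with an SAE by 1/30 = 0.033, or 3.3 percentage points. This is illustrative: it holds for any single subject. Only those with a successful trial are implanted, so the number who could need a revision after implantation may be below 30.
- *Follow-up.* For a non-device-related event starting t months after implant, follow-up lasts about 24 − t months. With onset at month 18, taken as an example, this is about 24 − 18 = 6 months. It is not a strict limit, because section 7.3 gives the 24-month visit a window of ± 2 weeks and calls the windows advisory.

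**The case against.** The strongest reply is that the exemption was meant to cover only the routine stay, and the text gives this some support. An SAE has to be an untoward occurrence, and a planned stay for a revision is not one. The reason given in the lead-in points the same way. A stay lengthened by, say, an infection can be described as the result of the infection and not of the revision. This stands as a possible reading, and it is why the point says that such an event may not be counted. It does not remove the problem, because the protocol does not state that reading and a multi-centre study needs one rule.

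A second reply is that little is lost. Much of this stands. The event remains an AE with severity and device causality. Section 8.1 keeps the legal reporting duties, and the exemption applies only for the purposes of this study. The follow-up gap needs several conditions at once, including a judgement that the event is not device-related. Section 8.2 counts implantation, deployment, operation and malfunction among the grounds for a device relationship, so many revision complications would probably be classed as related and followed until abated or stable. After study exit, subjects remain under their physician's standard care.

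A third reply is that section 9 plans no SAE proportion, threshold or safety test. That is correct: no planned statistic is shown to change. The point concerns which events are classified and reported as SAEs.

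A reader might go further and infer that the plan removes all revision complications from the SAE count, or that such events disappear from the safety data. The documents do not support either. Events serious on another criterion stay SAEs, new admissions are outside this exemption, and every AE is recorded regardless of causality.

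**Conclusion.** The point holds as an ambiguity with a real consequence. Taken literally, the first exemption in section 8.2 contradicts the SAE criterion in the same section for one class of event: a revision complication whose only serious feature is the prolonged stay. For that class, the SAE label and the 24-hour entry may be lost. Follow-up to resolution or stabilisation is lost only if the event is also judged not device-related and is unresolved at study end.

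The size cannot be estimated, because the documents give no rate for revisions or for prolonged stays. The conclusion rests on the protocol text alone and assumes that no site instruction or CRF guidance outside these documents imposes the narrower reading. It is worth correcting before the safety data are summarised. It does not bear on the primary pain outcome.

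**What to change.** Reconcile the exemption with the SAE definition by replacing the first exemption in section 8.2 with wording such as:

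> The planned, uncomplicated hospital stay for a revision procedure is not in itself an SAE; any complication of the revision, including one that prolongs the stay, is assessed against all SAE criteria and for relationship to the device.

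This keeps the reasonable purpose of not counting an expected stay. If the sponsor already intended the narrower reading, it merely states it.

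Optionally, add a yes/no item on hospitalisation or prolonged stay to the AE form, if the form does not already hold one, so that seriousness can be checked later whatever the label.

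The cost is one sentence of protocol text, possibly one form item, a few more SAE forms and a possibly less favourable SAE count.

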6.2 Summary of known and potential risks and benefits

A summary of the known and potential risks and benefits can be found in the accompanying manuals that are included in the packaging of the components. The general risks associated with the Spinal Modulation DRG Neurostimulator System are similar to those associated with other currently approved Spinal Cord Stimulator systems. Possible risks to the subjects include both device and procedural based risks. The most common side effects and risks are:

- Pain (where the needle is to be inserted)
- Pain caused by understimulation due to lead migration
- Pain over the implantable neurostimulator site (only applicable in Phase 2)
- Escalating pain
- Bleeding (where the needle has been inserted)
- Headache
- Infection
- Localized collection of serous (clear) fluid at injection site
- Discomfort during the treatment
- Allergic or rejection response to implant materials
- Constant pain at the lead site
- Stimulation of the chest wall
- Lead migration (movement) and/or local skin breakage
- Weakness
- Clumsiness
- Numbness
- Temporary muscle activation

Very rare risks and side effects include:

- Cerebral Spinal Fluid (CSF) leakage
- Tissue damage
- Nerve damage
- Spinal cord compression
- Swelling
- Paralysis
- Hematoma
- Seroma
- Sensory loss
- Skin erosion around the INS or leads
- Battery failure and/or battery leakage
- Lead breakage requiring replacement of the lead
- Hardware malfunction requiring replacement of the neurostimulator
- Pain from a non-injurious stimulus to the skin (allodynia)
- An exaggerated sense of pain (hyperesthesia)

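### Section 8.2 lists causality against the device only, discards the procedural link when both are suspected, and gives procedure-only events no stated category

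*Combined protocol and SAP*

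**What the plan says.** Section 2 names device safety as a secondary objective, without saying which events count towards it. Section 6.2 recognises two sources of harm: "Possible risks to the subjects include both device and procedural based risks".

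Section 8.2 lists what is recorded for every adverse event and serious adverse event: name, onset date, resolution date, severity and one causality item. That item reads "Relationship to study device: All AEs will have a study device causality assessment performed at the time of reporting the event". No item for relationship to the procedure appears in the list. The separate list of information for serious events asks for "SAE term, onset date, severity, and causal relationship" and does not say to what the causal relationship refers.

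Two statements in Section 8.2 then guide the causality rating. The first is "As stated in the ISO standards, adverse events classified as device-related should involve one of the following", followed by six items, one of which is "Implantation of the device". The second, after that list, is "If the Investigator feels the AE is related to the implant procedure and related or possibly related to the device, he/she should assign causality to" one of two device categories, related or possibly related.

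The resulting label is used twice. Section 8.2 sends events related to the system to the manufacturer's representatives under its vigilance rules. Section 8.3 follows device-related events until they abate or stabilise, whereas "All AEs determined to not be device related will be followed through the end of the study".

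**The concern.** The plan asks investigators to judge whether an event came from the implant procedure and treats this as distinct from whether it came from the device. The listed content gives that first judgement nowhere to be recorded. If both links are suspected, only the device link survives. If only the procedural link is suspected, the text does not say how to code it.

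In a post-market device study this distinction matters to the reader. Section 6.2's list of common risks puts needle-site pain, bleeding and infection alongside lead migration. Every treated subject has leads placed, and those who proceed have a second procedure, sometimes with new leads (Sections 5.1 and 7.3). A device-related tally that absorbs procedural events at some centres and not at others is hard to interpret. The same label also decides who is told about an event and may decide how long it is followed.

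**Working it through.** The plan states no event rate, no device-related rate and no sample size calculation, so there is no figure to reproduce. The check is a comparison of the text.

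**Step 1: what the two statements cover.** The six-item statement sets a condition that a device-related event should meet. It does not say that every event meeting the condition is device-related. The later sentence opens "If the Investigator feels the AE is related to the implant procedure and related or possibly related to the device", so it addresses only events with both links.

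**Step 2: apply them to the four possible combinations.**

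| Link to procedure | Link to device | Category under Section 8.2 | Procedural link kept in the listed data? |
|---|---|---|---|
| No | Yes or possible | Device category | Not applicable |
| Yes | Yes or possible | Device category, by the explicit sentence | No |
| Yes | No | Not stated | No |
| No | No | Not device-related | Not applicable |

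**Step 3: the unstated row.** Take bleeding at the needle site during implantation, with no suspicion of the hardware. An investigator who relies on the implantation item can call it device-related. Another may note that the later sentence requires a device link in addition to the procedural one, and call it not device-related. Nothing in Section 8 settles the choice. Section 8.4 states that there is no safety monitoring board, and no adjudication of causality is described.

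**Step 4: what depends on the choice.**
- Vigilance routing in Section 8.2 applies to events related to the system, so the two readings route the event differently.
- Under Section 8.3 a non-serious event is followed until it abates or stabilises on one reading, and through the end of the study on the other.
- Any table of device-related events would include it on one reading and omit it on the other.

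**Step 5: what does not depend on it.**
- Section 8.2 has all events reported regardless of causality, so the total count is the same.
- Section 8.3 follows serious events to resolution or stabilisation whatever their relationship to the device.

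**Step 6: scale.** Assume a per-subject device-related proportion is reported over the 30 subjects planned in Section 4.4. A subject whose only candidate event is procedure-only then moves it by 1/30 = 0.033, or 3.3 percentage points. The documents give no basis for assuming how many such subjects there will be, so no total shift is offered.

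**The case against.** A reader might infer that the two statements in Section 8.2 contradict each other. They do not. The first says what device-related events should involve, and the second says what to do if both links are present, not only if both are present. Both can be followed together. What is left is a gap and an ambiguity.

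A reader might also infer that no procedure causality is recorded anywhere. That cannot be established. Appendix A names the adverse event and serious adverse event forms (CRF-17 and CRF-18), but they are not reproduced, and Section 7.3 says copies of the forms are supplied for review. The causal relationship asked for with serious events is not limited to the device. The supportable statement is that the list in Section 8.2 names no such field.

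Two further inferences go too far. The device-related event rate is not stated to be the main safety output: Section 2 names device safety only in general terms, and Section 9 defines no causality-based rate. Nor is it true that surgical and system events cannot be told apart. Section 8.2 asks for event names that describe the pathophysiology, together with onset dates, and for serious events it also asks for the implant date. Needle-site bleeding and lead migration can be separated by term. What is lost is the investigator's own attribution, which matters most for events of mixed origin.

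Two more points can be made for the plan. Coding mixed events to the device errs towards over-counting device harm, which is a defensible caution. The follow-up difference affects only non-serious events still unresolved when follow-up ends, 24 months after implant for those who complete the study, so it will often make no difference. Both points stand. Neither supplies a category for procedure-only events or makes the vigilance routing consistent across investigators.

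**Conclusion.** The concern holds in limited form. The causality content listed in Section 8.2 covers the device only, events with both links lose their procedural attribution, and procedure-only events have no stated category. Any device-related summary, the vigilance routing and the follow-up of non-serious events therefore rest on each investigator's reading. The total event count and the follow-up of serious events do not.

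The size cannot be estimated from the documents. The figure of 3.3 percentage points per subject is only the weight of one subject in 30, and it assumes a per-subject proportion that the plan has not defined. The conclusion also assumes that CRF-17 and CRF-18 follow the list in Section 8.2. If they already carry a procedure field, the remaining defect is that the protocol neither mentions it nor says how to use it.

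**What to change.** 1. Check CRF-17 and CRF-18. Unless they already have one, add a relationship-to-procedure field that identifies the procedure (trial lead placement, neurostimulator implant or revision) and is rated independently of relationship to the device.
2. Replace the sentence on events with both links by an instruction to rate both, stating that a link to one does not remove a link to the other.
3. State how the implantation item in the six-item list maps onto the two fields.
4. Say which events make up the device-safety summary, and report device-related, procedure-related and both as separate rows.
5. Have the sponsor reconcile the vigilance and causality wording in Section 8.2 with the follow-up wording in Section 8.3, so that the label driving reporting and follow-up has one meaning. Which combination of the two fields should trigger each action is for the sponsor to decide.

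The cost is one extra form field, a few lines of protocol text and a slightly longer adverse event table. No additional visits are needed.
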